## 10.2 Secondary outcomes

These analyses will mirror those described for the primary endpoint above with the secondary outcomes as the end points of the analyses. These are only intended to be exploratory given the power of the study:

1. Time to a major or second minor relapse.

---

 Primary endpoint.

 Time measured from enrolment, in reality this corresponds to 20 months and 44 months post-randomisation.

 Close testing procedure will be implemented.

2. Time to a major relapse.

### 10.3 Censoring

Any patients who have not relapsed at study close will be censored. Further details of how relapse/censoring dates will be defined are given below:

Situation	Date of Relapse or Censoring	Outcome
No baseline assessments	Randomization	Censored
Relapse documented between scheduled visits	Unscheduled visit date	Relapsed
Drop-out with no relapse	Date of last assessment with no documented relapse	Censored
Treatment discontinuation for undocumented relapse	Date of last assessment with no documented relapse	Censored
Treatment discontinuation for toxicity or other reason, or protocol deviation	The patient will be followed up as per protocol and date of relapse or censoring observed accordingly	Relapsed/censored
Death due to relapse	Date of Death	Relapsed
Death due to other causes	Date of Death	Censored
Death or progression after more than one missed visit	Date of last assessment with no documented relapse	Censored

In the efficacy analysis, the date of the month 4 visit will be used as time-zero (i.e. randomisation). According to the protocol patients might be randomised in advance of the month 4 visit (provided they achieved disease remission by the month 3 visit), however maintenance therapy (with either treatment) was not allowed to be administered before the month 4 visit.

Treatment duration is taken to be strictly 20 months post-randomisation, i.e. date of the month 4 visit + 20 months, and not the actual time of the month 24 visit when the last visit was administered. This affords a common timeline for all patients, irrespective of time slippages in scheduled visits.

In the analysis, in accordance with the protocol, the censoring time will be taken to be:

1. If no baseline assessment: time of randomisation,
2. Otherwise, the latest date between:

 This endpoint was not originally included in the protocol (v4.0).

 For a more in-depth description of randomisation procedures and trial's timelines, including definitions of the Induction and Maintenance Phase, see Induction Phase SAP, section 9.1.1, and refer to the protocol, section 10.4.

- a. the last completed scheduled visit (or the last completed scheduled visit before more than two missed visits)
- b. death due to other causes (unscheduled visit)
- c. the common close date (for those patients whose end of trial visit, either month 42 or month 48, would have occurred after the common close).

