#### **16.5 Procedure to Account for Missing or Spurious Data**

A detailed statistical analysis plan will be produced before the final data base lock and this plan will include sub-group analyses. The only aspect of missing data that will affect the primary analysis is the handling of patients who drop out before the scheduled study close; the process for handling such events is given in the definition of the primary endpoint in section 9.6.1.

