**Table 1: Censoring rules**

Situation	Date of Relapse or Censoring	Outcome
No baseline assessments	Randomization	Censored
Relapse documented between scheduled visits	Unscheduled visit date	Relapsed
Drop-out with no relapse	Date of last assessment with no documented relapse	Censored
Treatment discontinuation for undocumented relapse	Date of last assessment with no documented relapse	Censored
Treatment discontinuation for toxicity or other reason, or protocol deviation	The patient will be followed up as per protocol and date of relapse or censoring observed accordingly	Relapsed/censored
Death due to relapse	Date of Death	Relapsed
Death due to other causes	Date of Death	Censored
Death or progression after more than one missed visit	Date of last assessment with no documented relapse	Censored

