Events happening between 6 and 12 months of the censoring date require further investigation. Depending on the last visit before any missing gaps, these events could fall after either one or two missed visits (e.g. an event 200 days after month 30 would happen after one missed visits, while an event 200 days after month 24

would happen after two missed visits). Thus the 12 months threshold is not strong enough to determine the outcome. The analysis code explicitly checks for such instances, which must then be adjudicated independently. None were found.

Likewise, by inspection, all deaths were by other causes and occurred before more than one missed visit, and thus no special considerations are needed (all patients who died were censored at the time of death).

An independent adjudication committee (blinded to treatment) will review all relapses and deaths. This will ensure that “deaths due to relapse” are recorded in the trial database as a relapse (i.e. there exists a corresponding relapse form). The censoring date of “deaths due to other causes” will also be verified in cases with more than one missed visit.

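### As worded, the latest-date censoring rule in SAP 10.3 would carry some drop-outs and non-relapse deaths forward to the common close as relapse-free, against Table 1 and protocol 9.6.1.

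*SAP*

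**What the plan says.** Two rules in the SAP date the censoring of the primary endpoint.

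**The table.** SAP Table 1 (section 5.2.1), its copy in SAP 10.3 and protocol 9.6.1 agree. For "Drop-out with no relapse" the date is "Date of last assessment with no documented relapse". Death from other causes is censored at the date of death. Protocol 16.5, on patients who leave before study close, states that "the process for handling such events is given in the definition of the primary endpoint in section 9.6.1". SAP 5.2.1 says the Table 1 rules will be implemented. It then lists last assessment, death and common close as sources of the censoring time, without saying which applies to whom.

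**The list.** Below the table, SAP 10.3 states how the censoring time will be taken in the analysis, and says this accords with the protocol. Apart from patients with no baseline assessment, the rule is "Otherwise, the latest date between" three candidates:

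- 2a: the last completed scheduled visit, or "the last completed scheduled visit before more than two missed visits";
- 2b: "death due to other causes (unscheduled visit");
- 2c: "the common close date (for those patients whose end of trial visit, either month 42 or month 48, would have occurred after" that close).

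Item 2c carries footnote 24. Its text, and the part of section 10.3 that follows it, are not in the version available for this review.

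**The concern.** Item 2c is defined by a planned visit date, and the visible text does not also require the patient to be under observation at the close. For anyone who meets it, the common close is always the latest of the three dates, so it overrides both the last visit and the date of death. The two rules in section 10.3 then give different dates for the same patient.

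This matters because the rule dates the primary endpoint. A patient carried forward stays in the risk set, with no possibility of a recorded relapse, for months in which nobody looked. That lowers the apparent hazard in the arm that loses more patients. Equal loss largely cancels; unequal loss does not. The trial is open label, so unequal withdrawal is possible, although the documents report none.

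**Working it through.** **Inputs.** 160 randomised 1:1; hazard ratio 0.42; 58 relapses; two-sided 5%; 90% power; drop-out up to 5% at 2 years; relapse-free 75% and 50% at 4 years (SAP 7, 6.3 and 10.1). Recruitment 24 months (protocol 16.1). Close 36 months after the last enrolment (SAP 8.1). Maximum 48 months in study (protocol synopsis). Time zero is the month 4 visit (SAP 5.2.1).

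**Step 1: the plan's own figure.** Schoenfeld events = 4 × (1.960 + 1.282)² / (ln 0.42)² = 42.03 / 0.7526 = 55.8, so 56. Power at 58 events is Φ(√58/2 × 0.8675 − 1.960) = Φ(1.343) = 0.91. The stated 58 events for 90% power is reproduced closely enough.

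**Step 2: who meets 2c.** With the first enrolment at calendar month 0, the close is 24 + 36 = 60. A patient enrolled at month e has the month 48 visit at e + 48, which falls after the close when e > 12. Under uniform accrual that is half of patients. Later enrolees are followed for less time, so their share of drop-outs is slightly lower: 5.2 of 11.0 expected at 5% in both arms, or 47%.

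**Step 3: one patient under both rules.** A patient enrolled at month 18 leaves just after the month 12 visit. The close is that patient's month 60 − 18 = 42, and the month 48 visit would come later, so 2c is met.

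- Table 1: censored at 12 − 4 = 8 months after randomisation.
- Latest of 2a to 2c: censored at 42 − 4 = 38 months.
- Difference: 30 unobserved months counted as relapse-free.

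Over all affected drop-outs at the planned rate, the mean added time is about 23 months.

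**Step 4: deaths.** The same patient, dying of another cause at month 12, would be censored at the close, after death. Table 1 gives the date of death. Later in section 10.3 the SAP reports that "all patients who died were censored at the time of death". If any of those patients met 2c, what was done already differs from the written list.

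**Step 5: effect on the hazard ratio.** Large-sample simulation with one treatment covariate: uniform accrual, exponential relapse (−ln 0.75/48 and −ln 0.50/48 per month, ratio 0.415; 50% in both arms for the null), exponential drop-out, last assessment taken from the visit schedule. Drop-out rates other than 5% are assumptions.

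| Drop-out at 2 years, rituximab / control | HR, Table 1 | HR, literal list | Null HR, Table 1 | Null HR, literal list |
|---|---|---|---|---|
| 5% / 5% (planned) | 0.417 | 0.417 | 0.995 | 0.995 |
| 15% / 5% | 0.42 | 0.40 | 1.01 | 0.96 |
| 20% / 5% | 0.423 | 0.393 | 1.013 | 0.934 |
| 5% / 20% | 0.408 | 0.445 | 0.985 | 1.068 |

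The small departures from 0.415 and 1 under Table 1 arise mainly because a drop-out is dated back to the preceding visit. In 4,000 null trials of 160 patients at 20%/5%, the type I error was 5.7% under Table 1 and 6.1% under the literal list. The simulation error is about √(0.06 × 0.94/4000) = 0.4 points, so those two are not distinguishable. At 30%/5% they were 4.5% and 6.6%.

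Most of the carried-forward time lies beyond 20 months, so the post-treatment sub-hypothesis in SAP 10.1 moves more: at 15%/5% its null ratio goes from 1.01 to 0.93.

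**The case against.** The strongest reply is that the list was never meant to replace the table. SAP 5.2.1 says Table 1 will be implemented, section 10.3 reprints it directly above the list, and the list claims to follow the protocol. Item 2c reads naturally as administrative censoring of patients whose final visit was pre-empted by the close. The missed-visits clause in 2a shows an intention to stop at gaps, which the literal reading would defeat. Footnote 24 and the unseen text may state the restriction. The later reference in 10.3 to a 12-month threshold, not defined in the visible part of that section, shows that some operational detail is there. The statement on deaths also fits the Table 1 reading.

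Most of this stands as evidence of intent. It does not remove the conflict. No visible sentence says that the table prevails, and the list is what a programmer would code from.

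On size, the reply is also largely right. Protocol 10.6 expects withdrawal to be rare and keeps patients who stop treatment in follow-up, so they are not drop-outs. With 58 events the standard error of the log hazard ratio is about 2/√58 = 0.263. The 15%/5% shift is ln(0.42/0.40) = 0.049, about 0.19 of a standard error.

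A reader might infer more: that every drop-out is carried to the close, or that the primary result is biased. Neither is supported. Item 2c reaches only patients whose month 42 or 48 visit would fall after the close. Nothing in the documents shows that the code carried anyone forward, or that drop-out differed between arms.

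**Conclusion.** The visible wording of SAP 10.3, item 2, conflicts with the table in the same section, with SAP Table 1 and 5.2.1, and with protocol 9.6.1. It does so for drop-outs and non-relapse deaths among later enrolees, roughly half of drop-outs under uniform accrual. It should be corrected because it dates the primary endpoint.

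The numerical effect is nil at the planned, balanced 5% drop-out. It is modest under unequal loss: about 0.42 to 0.40 (null 1.01 to 0.96) at 15% against 5%, and 0.42 to 0.39 (null 1.01 to 0.93) at 20% against 5%. It favours whichever arm loses more patients. These figures rest on assumed drop-out rates, exponential times and uniform accrual, and the model omits the stratification covariates.

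The conclusion is conditional on text not seen. If footnote 24 or the rest of section 10.3 already limits 2c to patients still in follow-up, what remains is to move that limit into the rule itself.

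**What to change.** First read footnote 24, the full text of section 10.3 and the analysis code. Then:

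1. Reword item 2 so that the common close applies only to patients not withdrawn from the trial, lost to follow-up or dead before that date. All others are censored at the last assessment with no documented relapse, or at the date of death, as in Table 1.
2. State that Table 1 prevails if the list and the table differ. While editing, reconcile the two-missed-visits limit in 2a with the limit of more than one missed visit in Table 1.
3. Confirm that the code applies the same condition, and list every patient censored at the common close whose last completed visit or date of death is earlier than their schedule would imply.

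The cost is one sentence in the SAP, one condition in the code and a short listing. No new data are needed.

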Events happening between 6 and 12 months of the censoring date require further investigation. Depending on the last visit before any missing gaps, these events could fall after either one or two missed visits (e.g. an event 200 days after month 30 would happen after one missed visits, while an event 200 days after month 24

would happen after two missed visits). Thus the 12 months threshold is not strong enough to determine the outcome. The analysis code explicitly checks for such instances, which must then be adjudicated independently. None were found.

Likewise, by inspection, all deaths were by other causes and occurred before more than one missed visit, and thus no special considerations are needed (all patients who died were censored at the time of death).

An independent adjudication committee (blinded to treatment) will review all relapses and deaths. This will ensure that “deaths due to relapse” are recorded in the trial database as a relapse (i.e. there exists a corresponding relapse form). The censoring date of “deaths due to other causes” will also be verified in cases with more than one missed visit.

## 11 Safety Analyses

### 11.1 Serious Adverse Events

All serious adverse events (SAE), including serious adverse drug reactions will be reported according to guidance in sections 13.4 and 13.5 of the protocol.

All Serious Adverse Events must be reported to the central trials co-ordinator or trial physician in Cambridge within 24 hours of the investigator becoming aware of the event and will be entered in a separate database. Individual SAEs will be assessed by the trial physician, and if advice is needed, this will be sought from one of the CIs, blinding them to treatment allocation. Monthly SAE listings, blinded to treatment allocation, will be reviewed by both CIs however. The Sponsor has to keep detailed records of all SAEs reported to them by the trial team.

Frequency tables for all SAEs will be reported using the safety population and stratified by both treatment arm and induction regimen as well as their interaction.

Separate tables will report:

- SAEs where date of onset occurred after randomisation
- SAEs occurring during treatment (up to 20 months after randomisation)

---

 SAEs occurring during the induction period (prior to randomisation) were reported separately, see Induction Phase SAP and report.

- SAEs occurring after treatment ended (from 20 months after randomisation onwards)

Additionally, counts of subjects and events stratified by relatedness (Unrelated/Related) will be reported, grouped by System Organ Class, High Level Group Term and Preferred Term based on the MedDRA code.

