Concomitant Therapy	
Glucocorticoids at induction
 
For all glucocorticoid dosing, prednisone may be substituted for prednisolone.
 
The investigator may choose one of two permitted GC regimens:
 
Oral prednisone (prednisolone will be allowed), commencing at 1.0mg/kg/day (maximum 60 mg/day), or 0.5mg/kg/day (maximum 30 mg/day), both reducing to 10mg/day by month 3 (See schedule 1, pg. 26).
 
Maximum daily dose of GC is 60 mg prednisone in week 0. Round down to the nearest 5 mg above 20 mg. Round down to the nearest 2.5 mg below 20 mg. GC to be administered in a single daily dose.
 
Intravenous (IV) GCs are not mandated by the protocol. At the investigator's discretion, patients may receive up to a maximum cumulative dose of 3000mg IV methylprednisolone, between 14 days prior to enrolment and 7 days after enrolment.
 
Glucocorticoids in Maintenance Phase:
 
A GC dose of prednisolone 10 mg/day or less is a requirement for randomisation. GC reduces to 5 mg/day by month 6, according to schedule 2 (pg. 26). At month 16, GC dose is reduced to 2.5mg/day and at month 20 GC are completely withdrawn.

Maximum Treatment Duration	Treatment is protocolised for the entire duration of the study, until the common close date, when the final patient recruited has completed 36 months within the study or until the patient has completed 48 months on study whichever the sooner. Patients in the rituximab arm will receive treatment until

	month 20, and those in the azathioprine arm until month 27.
Summary of Study Procedures	
Screening:	Procedures to establish inclusion/exclusion criteria.
Baseline:	Baseline data will include: 
 
1. Date of birth, sex, limited medical history
 
2. Medications, including prior AAV treatments
 
3. Height/weight
 
4. Urinary HCG in women of child bearing potential at screening or on Day 1 of rituximab treatment
 
5. Disease activity assessment (BVAS/WG)
 
6. Disease related damage assessment (CDA)
 
7. Patient self-reported SF-36 questionnaire, EQ5D questionnaire and PROMIS questionnaires.
 

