#### 9.5.2 Secondary objectives

To demonstrate

1. Sustained disease remission beyond the 24 month treatment period
2. Long term safety of rituximab administration
3. The optimal remission maintenance therapy in AAV following induction of disease remission with rituximab

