### ii. Administration

The target dose is 2mg/kg. The maximum daily dose is 200mg. This should be continued until month 24. The dose should then be reduced by 50% and azathioprine completely withdrawn at month 27. The dose should be rounded down to the nearest 25mg. The dose may vary on alternate days e.g. 100mg one day, 150mg the next for patients on an overall dose of 125mg daily.

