#### 5.2.1 Primary endpoint

The primary endpoint is the time to disease relapse (either minor or major relapse) from randomisation. Any patients who have not relapsed at study close will be censored. Further details of how relapse/censoring dates will be defined are given below (Table 1).

In the efficacy analysis, the date of the month 4 visit will be used as time-zero (i.e. randomisation). According to the protocol, patients might be randomised in advance of the month 4 visit (provided they achieved disease remission by the month 3 visit), however maintenance therapy (with either treatment) was not allowed to be administered before the month 4 visit.

---

 For a more in-depth description of randomisation procedures and trial's timelines, including definitions of the induction and maintenance phase, see Induction Phase SAP, section 9.1.1, and refer to the protocol, section 10.4.

Treatment duration is taken to be strictly 20 months post-randomisation, i.e. date of the month 4 visit + 20 months, and not the actual time of the month 24 visit when the last visit was administered. This affords a common timeline for all patients, irrespective of time slippages in the schedule of visits.

In the analysis, the censoring rules detailed in Table 1 will be implemented. Censoring time will be taken from the last assessment with no documented relapse (scheduled visit), the date of death (unscheduled visit) or the common close date. The time of relapse will be taken from the relapse form (unscheduled visit). Further particulars are detailed in section 10.3.

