### 10.1 Primary efficacy analysis

The primary efficacy outcome measure of the trial is relapse-free survival, where a relapse is either major or minor (see definitions above). **The primary analysis will be a Cox regression model adjusted for the stratification factors (ANCA type, relapse severity and prednisone induction regimen) for the difference in the distribution of relapse-free survival between the rituximab arm and the azathioprine (control) arm (two-sided at  $\alpha$ -level of 5%).** Assuming a proportional hazard holds, the hazard ratio together with the 95% confidence interval will be estimated using a Cox regression model adjusted for the stratification factors.

There will be a closed testing procedure, first the null hypothesis will be tested for a hazard ratio of 1 at all time points. If this is rejected at a 5% level then two further sub-hypothesis will be examined using time-varying covariates:

1. A hazard ratio of 1 up to 20 months post-randomisation (i.e. during treatment).
2. A hazard ratio of 1 after 20 months post-randomisation (i.e. post-treatment).

Kaplan-Meier estimates for relapse-free survival at 24 and 48 months and median relapse-free survival with the corresponding 95% confidence intervals by treatment allocation will be presented.

Additional analyses will consider in turn the interaction of treatment with each of the three stratification variables, i.e. ANCA type, relapse severity and induction regimen. Frequency tables and Kaplan-Meier plots, as well hazard ratios and 95%

---

 Time measured from enrolment, in reality this corresponds to 20 months and 44 months post-randomisation.

confidence intervals of a Cox proportional hazard model including interactions will be presented. These results are to be taken as exploratory only, as these analyses were not planned in the protocol, are likely under-powered and are not adjusted for multiple comparisons.

The following tables and figures will be reported, taking into account events occurring after randomisation (i.e. excluding the induction phase):

- No. of relapses:
  - a) by type (major or minor)
  - b) by phase (during treatment or post-treatment)
  - c) per participant
- No. of participants with a relapse (major or minor) by type at:
  - a) All time points
  - b) During treatment (up to month 20 post-randomisation)
  - c) Post-treatment (after 20 months post-randomisation)

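### The SAP ends treatment at month 24 in both arms, but control patients still on protocolised treatment take a half dose to month 27, so its post-treatment safety tables, and possibly its post-treatment relapse results, include on-drug control time

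*SAP*

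**What the plan says.** **SAP.** Section 5.2.1, repeated in 10.3, sets one rule for everyone: "Treatment duration is taken to be strictly 20 months post-randomisation, i.e. date of the month 4 visit + 20 months". Section 10.1 uses that boundary for the second sub-hypothesis of the closed test, "A hazard ratio of 1 after 20 months post-randomisation (i.e. post-treatment", and for the relapse counts by phase. Section 11.1 uses it for serious adverse events, with one table headed "SAEs occurring during treatment (up to 20 months after randomisation" and another headed "SAEs occurring after treatment ended (from 20 months after randomisation onwards". The reason given is a common timeline that is not disturbed by late visits. No section handles the control taper separately.

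**Protocol.** Treatment ends at different times by arm. The synopsis says that rituximab patients are treated until "month 20, and those in the azathioprine arm until month 27". Section 11.2 says of azathioprine: "The dose should then be reduced by 50% and azathioprine completely withdrawn at month 27", where the reduction takes place at month 24. Sections 11.3 and 11.4 say the same for methotrexate and mycophenolate mofetil. Section 11.1.4 ends rituximab at month 20, and section 11.5.1 withdraws glucocorticoids at month 20 in both arms.

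**The SAP against itself.** SAP 9.10 restates the protocol's 27-month control treatment period with tapering after month 24, which does not fit the rule in 5.2.1. SAP 8.9 and protocol 16.1 split the relapse hazard ratio at 24 months post-randomisation, not at 20.

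**The concern.** A period labelled as after treatment should be off protocolised drug in both arms. From month 24 to month 27 it is not. Control patients still on protocolised treatment are scheduled to take half their dose, while rituximab patients are 4 to 7 months past their last infusion.

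Two outputs are exposed. The first is the table of serious adverse events after treatment, which compares on-drug control time with time after the last infusion under a heading that says both arms have stopped. The second is the late relapse comparison. Protocol 9.5.2 lists as an objective "Sustained disease remission beyond the 24 month treatment period", and the late hazard ratio is a natural place to look for evidence on it. If the first months of that window include drug in one arm, the ratio does not compare two untreated groups.

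**Working it through.** **1. The plan's boundary.** Time zero is the month 4 visit, and 4 + 20 = month 24 from enrolment. This agrees with the footnote in SAP 10.1 that equates 24 months from enrolment with 20 months post-randomisation.

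**2. The control stop on the same clock.** 27 − 4 = 23 months post-randomisation. The gap is 23 − 20 = 3 months, in the control arm only.

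**3. The competing relapse split.** SAP 8.9 and protocol 16.1 use 24 months post-randomisation, and 24 + 4 = month 28. Protocolised control drug has stopped by then. The relapse part of this point therefore arises only if SAP 10.1 governs. For serious adverse events the 20-month boundary is the only one given.

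**4. Share of follow-up.** Protocol 9.4 gives 12 to 24 months of follow-up after month 24.

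- Minimum follow-up: 3/12 = 25%.
- Maximum follow-up: 3/24 = 12.5%.
- Average: assume uniform accrual over 24 months, closure 36 months after the last enrolment, and a 48-month cap. The first half of patients have 24 months after month 24; the second half average 18. The mean is 0.5 × 24 + 0.5 × 18 = 21 months, and 3/21 = 14%.

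**5. Expected control relapses in the window.** Inputs from SAP section 7 are 160 patients, 80 per arm, relapse-free rates of 50% and 75% at 4 years, and 5% drop-out at 2 years. They are coherent with the plan's design figures: ln 0.75 / ln 0.50 = 0.415, against a stated hazard ratio of 0.42. The Schoenfeld formula gives 56 events for 90% power, against the stated 58, and 58 events give 91.0% power.

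Assume exponential times with 4 years read as 48 months from time zero:

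- control hazard λ = −ln 0.50 / 48 = 0.0144 per month
- drop-out hazard d = −ln 0.95 / 24 = 0.0021 per month
- relapses between a and b = 80 × λ/(λ + d) × [e^−(λ+d)a − e^−(λ+d)b]

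| Control relapses | Follow-up to month 36 | Follow-up to month 48 |
|---|---|---|
| Months 24–27 | 2.43 | 2.43 |
| All after month 24 | 9.02 | 16.42 |
| Share | 27% | 15% |

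Reading 4 years as 44 months from time zero gives 2.57 relapses in the window, out of 9.52 or 17.19. The shares are again 27% and 15%.

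**6. Possible effect on the late hazard ratio.** Let the control hazard in months 24–27 be k times its later value, and the rituximab hazard m times its later value. With a later ratio of 0.415, the ratio inside the window is 0.415 × m/k. Neither k nor m is in the documents.

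Take m = 1 (no residual rituximab effect) and pool the log ratios weighted by expected relapses:

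| k (assumed) | Late ratio, follow-up to month 36 | Late ratio, follow-up to month 48 |
|---|---|---|
| 1 | 0.415 | 0.415 |
| 0.75 | 0.444 | 0.430 |
| 0.5 | 0.475 | 0.445 |
| 0.25 | 0.513 | 0.462 |

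If m = k, the ratio in the window is again 0.415 and the shift disappears. If m is smaller than k, the shift goes the other way.

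**7. Serious adverse events.** The documents give no event rate, so the number misclassified cannot be estimated. The misclassification does not depend on whether the taper works.

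**The case against.** **Month 24 is the design's own boundary.** The protocol defines maintenance as months 4 to 24, and its objective refers to the period beyond 24 months. A comparison after month 24 answers that objective as worded, with the taper as part of the control strategy. This stands as a reason to keep the planned analysis. It does not make the off-treatment label true for control patients who are still taking drug.

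**Drug given is not drug effect.** A reader might infer that only the control arm is protected in months 24 to 27, and so that the late hazard ratio is biased against rituximab. The documents do not support that. Protocol 11.1 says B cell return typically begins after four months, which is about month 24 after the month 20 dose, so some residual rituximab effect cannot be excluded. Both effects are unquantified, and step 6 shows that they can cancel or reverse.

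**The relapse part may vanish.** If the split in SAP 8.9 and protocol 16.1 governs, it does. This stands, and it is a further reason to settle the split.

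**The safety effect is mainly labelling.** No event is lost: SAP 11.1 also tabulates all post-randomisation serious adverse events and gives counts by relatedness. Patients with a major or second minor relapse before month 24 have already left protocolised treatment (protocol 11.6), so not every control patient is on drug in the window. Both observations limit the effect. Neither removes it.

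**Conclusion.** The point holds as a misclassification in the SAP's period rule. For control patients still on protocolised treatment, 3 months of scheduled half-dose drug are labelled as after treatment. This is certain for the serious adverse event tables in SAP 11.1. It applies to the relapse counts and late hazard ratio only if the split in SAP 10.1 governs.

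The window is 12.5% to 25% of planned follow-up after month 24, about 14% on average under uniform accrual. Under the design's own rates with exponential times, it holds roughly 15% to 27% of expected control relapses after month 24. These figures measure exposure to the problem, not bias. The hazard ratios in step 6 illustrate assumed taper effects and are not estimates.

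A reader might go further and conclude that the trial's main result is compromised. It is not: the first step of the closed test uses all time from randomisation, so the boundary does not enter it. The design event count is also unaffected.

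**What to change.** 1. In SAP 11.1 and in the relapse counts of SAP 10.1, show 20 to 23 months after time zero as a separate taper window in both arms. Use the off-treatment label only from 23 months. A separate window is better than moving the boundary to month 27 for everyone, which would count rituximab patients up to 7 months past their last infusion as on treatment.
2. Keep the closed test as planned. Add a hazard ratio starting at 23 months, labelled as a sensitivity analysis outside the closed test, and report it beside any statement about benefit off treatment.
3. Amend "Treatment duration is taken to be strictly 20 months post-randomisation" in SAP 5.2.1 and 10.3 to say that the control taper runs to month 27.
4. Reconcile the relapse split in SAP 10.1 (month 24) with SAP 8.9 and protocol 16.1 (month 28).

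The cost is SAP wording and one extra cut-point in the code. A month 27 visit is already scheduled, with control doses recorded, so no new data and no change to treatment rules are needed. The stricter window has fewer events. Under the assumptions of step 5, with 48 months as the 4-year point, expected relapses in both arms fall from 13.7 to 10.0 with follow-up to month 36, and from 25.3 to 21.7 with follow-up to month 48. Power at a hazard ratio of 0.42 falls from 36% to 28% and from 59% to 52%. That is a reason to present the 23-month ratio as an estimate with its interval, and not as a replacement test.
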